13.2.7. Figures

Figure 14.3.2.1: Laboratory data: Subject profile plots over time

Subject profile plots over time, with each lab test and treatment group on a new page but with all subjects of one treatment group on the same plot. Any unscheduled results will also be part of this plot.

Population: safety.

Figure 14.3.2.2: Laboratory data: Mean (+/- SE) plots of the actual values over time

Mean (with SE) plots of the actual values over time, with each lab test on a new page but with all treatment groups on the same plot using different plot symbols. Unscheduled results will not be part of this plot.

Population: safety.

Figure 14.3.2.3: Laboratory data: Mean (+/- SE) plots of the changes from baseline over time

Mean (with SE) plots of the changes from baseline over time, with each lab test on a new page but with all treatment groups on the same plot using different plot symbols. Unscheduled results will not be part of this plot. With a horizontal reference line at zero, indicating no change. Plots will start with a zero mean at baseline.

Population: safety.

13.2.8. Listings

All listings will contain next to the actual data (raw and changes) the following parameters:

- an abnormality L/H flag
- the test's normal range
- a clinical relevance flag

Listing 16.2.11.1: Laboratory data: Full listing

Listing per treatment group, per subject and per time point of all data.

Population: safety.

Listing 16.2.11.2: Laboratory data: Abnormalities listing

Listing per treatment group, per subject and per time point of all post-baseline time points scored as out-of-normal-range or clinically significant, plus also the baseline reference time point.

Population: safety.

13.3. ECG

13.3.1. Available Data

Available parameters: HR (heart rate), RR, QRS, PR and QT (corrected QT).

13.3.2. Calculated Parameters

The QTc will always be derived during the statistical analysis, even when already available in the database. The value in the database will not be used in the analysis.

The QTc will be calculated using the following formulae:

- Fridericia's cube-root corrected QT (Fridericia, 1920):

$$\begin{aligned} \text{QTcF (ms)} &= \text{QT (ms)} \times \sqrt[3]{\frac{1000}{\text{RR(ms)}}} \\ \text{QTcF (ms)} &= \text{QT (ms)} \times \sqrt[3]{\frac{\text{HR(bpm)}}{60}} \end{aligned}$$

The formula using RR is preferred. In case no RR is available, at a subject level, the formula using HR will be applied for all subjects. Derived QTc values will be rounded to the nearest first decimal before deriving changes from baseline and categories.

13.3.3. Baseline and Change from Baseline

The baseline is defined as the last nonmissing value prior to dosing. Baseline will be determined per ECG parameter individually. It is recognized that baseline parameters may thus come from more than one ECG reading.

The change from baseline will be calculated for all post-baseline time points as:

Change from baseline at time point t = value at time point t – baseline value.

13.3.4. Normal Ranges

QT and QTc parameters: first round the value as described above, and then apply the following categorizations:

- of the actual values:
 - ≤ 450 ms,
 - $]450,480]$ ms,
 - $]480,500]$ ms,
 - >500 ms;
- of the changes from baseline:
 - ≤ 30 ms (including all decreases in QT),
 - $]30,60]$ ms,
 - >60 ms.

13.3.5. Worst-case Abnormality of QT and QTc

Derived per parameter separately.

All nonmissing postbaseline values (including unscheduled measurements and follow-up measurements) will be used to derive the following worst-case. The worst-case is the largest nonmissing post-baseline value and the largest non-missing change from baseline.

13.3.6. Tables

No formal inferential statistics (p-values) will be derived.

Table 14.3.3.1: ECG: Descriptive statistics of the actual values per time point

Descriptive statistics of the actual values per test and unit, treatment group and time point.

Population: safety.

Table 14.3.3.2: ECG: Descriptive statistics of the changes from baseline per time point

Descriptive statistics of the changes from baseline per test and unit, treatment group and time point. The actual value at baseline will also be presented in this table.

Population: safety.

Table 14.3.3.3: ECG: Shift table according to the QT normal range per time point

Shift table per test, treatment group and time point. The table will present the shift in abnormality at each post-baseline time point (including worst-case) versus the baseline abnormality. Parameters: QT, QTcF.

Population: safety.

Table 14.3.3.4: ECG: Treatment-emergent QT abnormalities per time point

Frequency table of the treatment-emergent abnormalities per parameter, treatment group and time point (including worst-case). A post-baseline abnormality is considered treatment-emergent if it is higher than the baseline result. Parameters: QT, QTcF.

Population: safety.

Table 14.3.3.5: ECG: Treatment-emergent abnormal change in QT per time point

Frequency table per test, treatment group and time point (including worst-case). The table will present the abnormality of the changes at each post-baseline time point according to the classifications of section 13.3.4 Parameters: QT, QTcF.

Population: safety.

Table 14.3.3.6: ECG: Frequency table of the eCRF ECG interpretation per time point

Frequency table per treatment group and time point of the ECG interpretation scores as recorded in the eCRF. Interpretation scores are:

- Cardiac conduction disorders;
- Rate and rhythm disorders;
- Supraventricular arrhythmias;
- Ventricular arrhythmias.

Note that more than one of these items can be ticked.

Population: safety.

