5.2.7. Removal of Subjects From Therapy or Assessments

The investigator will comprehensively investigate safety data (e.g. clinical laboratory parameters and AEs) to decide whether to stop dosing of individual subjects.

A subject may be discontinued from the study at any time without the subject's consent if the investigator or sponsor determines that it is not in the best interest of the subject to continue participation.

The investigator may decide to withdraw a subject from treatment (preferably after consultation with the sponsor's medical lead) for any of the following reasons:

- Subject request.
- Use of concurrent therapy that was not permitted.
- Noncompliance with the study drug.
- Noncompliance with the study procedures.
- Lost to follow-up.
- Serious or severe AEs.
- Investigator request.
- Sponsor request.

Treatment with GLPG2222 will be discontinued and the subject will be withdrawn from the study (preferably after discussion with the sponsor's medical lead) for any of the following conditions:

- Life-threatening AE or an SAE that places the subject at immediate risk.
- Serious infection requiring parenteral antimicrobial therapy and/or hospitalization.
- Pregnancy.
- Arrhythmia or conduction abnormality, including but not limited to prolonged QTcF, where the severity is categorized as CTCAE Grade 3 or higher.
- Confirmed increase in liver function tests, defined as:
 - Two sequential AST and/or ALT elevations $> 3 \times$ ULN, with at least 1 total bilirubin value $> 2 \times$ ULN.
 - Two sequential AST and/or ALT elevations $> 3 \times$ ULN, with 2 sequential increases of alkaline phosphatase and/or GGT $> 3 \times$ ULN.
 - Two sequential AST and/or ALT elevations $> 3 \times$ ULN, accompanied by clinical signs or symptoms suggestive for hepatic injury.

- Two sequential AST and/or ALT elevations $> 5 \times$ ULN, regardless of total bilirubin value and/or alkaline phosphatase and/or GGT values and/or clinical signs or symptoms suggestive for hepatic injury.

If one of the above is detected, retesting for these laboratory parameters must be performed to determine if discontinuation criteria are confirmed. If confirmed, the sponsor's medical lead must be contacted and the subject will be withdrawn from the study. In any case, additional investigations are needed (such as: assessment of alcohol or recreational drugs intake, hepatitis infection).

- The sponsor or Regulatory Authorities close the study.

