4.3. ALGORITHM OF ALLOCATING VISITS TO TIME WINDOWS

All visits (including unscheduled visits but excluding visits without data) will be placed into time windows according to their relative day (DY) in the study, according to the following allocation table:

Visits falling really late in the study will be allocated to a “>Day 29” interval, and will not be shown in tables nor figures, but will only be listed.

Time point label	Target day	Interval lower bound	Interval upper bound
Screening ³	NAP ⁴	NAP ⁴	NAP ⁴
Baseline ¹	NAP ⁴	NAP ⁴	NAP ⁴
Day 1 post-dose ³	NAP ⁴	NAP ⁴	NAP ⁴
Day 15	15	2	21
Day 29	29	22	36
>Day 29 ²	NAP ⁴	37	$+\infty$
Follow-up ³	11-17 days after last visit	NAP ⁴	NAP ⁴

¹ The actual baseline reference value will be determined per parameter as the last available pre-dosing data point, so might differ from this “baseline” visit interval.

² Visits falling really late in the study (relative day > 36; excluding the follow-up visit) will be allocated to a “>Day 29” interval, and will not be shown in tables nor figures, but will only be listed.

³ For the screening, day1 post-dose (vital signs) and follow-up visits, no time window is defined. The visit as recorded in the CRF will be used.

⁴ NAP = Not applicable

For efficacy, PD data, all by-time-point summaries will be based on the visit indicated on the subject’s CRF and will not be placed in time windows.

Tables, figures and listings will present the time points, not the visits.

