4.4. SELECTION OF VISITS

It is possible that more than one visit gets allocated into the same time window. In that case, only one visit will be selected for analysis tables and figures. The nonselected visit(s) will only be listed, and flagged as use=no.

The visit with a relative day (DY) closest to the target day will be selected. If there are multiple visits at the same distance of the scheduled visit day (meaning: equal ABS(DY – target day)), then the one latest in time is selected.

In case of multiple screening visits, the last pre-baseline screening measurement (the last visit happening before the scheduled 'Day 1 predose') is selected for analysis. This value (not the original first screening value) was also used in the clinical center to include the subject in the study.

In case more than one parameter is measured per time point (e.g. for lab), the selection is performed per parameter and per time point, not per “sample” and per time point. Missing values are removed before the selection is made.

As baseline reference point, the last nonmissing pre-dosing value will be used. This is normally the scheduled baseline itself. A missing scheduled baseline value will be imputed with the last nonmissing value of a preceding pre-dosing visit. This can be a screening visit or an unscheduled visit prior to the first dose of study medication. If there is an unscheduled measurement taken after the scheduled baseline, before the first dose of study drug, then this unscheduled measurement will be used instead of the scheduled baseline. If there is an

unscheduled measurement at the same datetime as the scheduled baseline, then it is assumed that the unscheduled measurement is taken after the scheduled baseline.

In case the screening visit is used to impute the baseline, the original screening visit as well as the imputed baseline will be presented in the tables. In the listings, only original screening data will be shown: the original screening visit will be shown and flagged as “reference” visit. The imputed baseline will not be shown.

In case an unscheduled visit is used to impute the baseline, the visit will be renamed to “baseline”. The imputed baseline will be presented in the tables. In the listings, the original unscheduled data will be shown and flagged as “reference” visit.

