4.5. HANDLING OF UNSCHEDULED ASSESSMENTS

If there is an unscheduled measurement at the same datetime as a scheduled visit, then it is assumed that the unscheduled measurement is taken after the scheduled visit.

Unscheduled measurements prior to use of the study drug: see section 4.4.

Unscheduled measurements after the first dose of study drug: place into time window (section 4.3) and selection will be made according rules defined in section 4.4.

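### The only ECG table of arrhythmia and conduction findings (SAP Table 14.3.3.6) has no within-subject shift from baseline and no any-post-baseline row

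*SAP*

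**What the plan says.** SAP 13.3.6 describes Table 14.3.3.6 as "Frequency table per treatment group and time point of the ECG interpretation scores as recorded in the eCRF". It names four items, more than one of which can be ticked for the same ECG. It states no shift, no treatment-emergent rule and no worst-case.

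The other categorical ECG tables in that section are built differently. Table 14.3.3.3 shows the "shift in abnormality at each post-baseline time point (including worst-case) versus the baseline abnormality. Parameters: QT, QTcF". Table 14.3.3.4 adds a rule for what is new: "A post-baseline abnormality is considered treatment-emergent if it is higher than the baseline result. Parameters: QT, QTcF". Table 14.3.3.5 classifies changes and also includes a worst-case. The worst-case itself is set out in SAP 13.3.5, whose heading limits it to QT and QTc: "All nonmissing postbaseline values (including unscheduled measurements and follow-up measurements) will be used to derive the following worst-case". It is then defined as the largest value and the largest change.

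For ECGs, as for other safety data, SAP 4.3 allocates visits to windows by relative day (DY): DY 2 to 21 for Day 15 and DY 22 to 36 for Day 29. The exemption from windowing in that section covers efficacy and PD data only. For unscheduled assessments after the first dose, SAP 4.5 says: "place into time window (section 4.3) and selection will be made according rules defined in section 4.4". SAP 4.4 keeps the visit closest to the target day, or the latest on a tie. Of the others it says: "The nonselected visit(s) will only be listed, and flagged as use=no".

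**The concern.** Changes over time in the 12-lead ECG are part of the primary endpoint (Protocol 4.1). Protocol 5.2.7 also makes "Arrhythmia or conduction abnormality, including but not limited to prolonged QTcF" a withdrawal condition at CTCAE Grade 3 or higher. A reader will turn to Table 14.3.3.6 to see whether such findings arose on treatment, and the table as described cannot answer that in two respects.

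First, counts at separate time points do not show whether the same subjects are affected. A minor, stable conduction finding that was present before dosing appears at every later visit in its group, indistinguishable from a new one.

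Second, one ECG per subject and window enters the table. Without a row that draws on every post-baseline ECG, a finding seen only on a nonselected ECG is absent from this summary. The flow chart schedules an ECG at early discontinuation, but the allocation table in SAP 4.3 has no early-discontinuation time point, so that ECG competes for a window like any other. The table could then omit the ECG taken when a subject withdrew.

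**Working it through.** The plan gives no figure to reproduce here, so the check is a comparison of table definitions followed by an enumeration of the selection rule.

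**Comparison across the SAP's safety tables**

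| Data | Shift versus baseline | Treatment-emergent table | Worst-case |
|---|---|---|---|
| QT, QTcF (13.3.6) | 14.3.3.3 | 14.3.3.4 | yes |
| Laboratory (13.2.6) | 14.3.2.3; categorical tests in 14.3.2.5 | 14.3.2.4 | yes (14.3.2.3, 14.3.2.4) |
| Vital signs (13.4.5) | 14.3.4.3 | 14.3.4.4 | yes |
| Pulse oximetry (13.5.5) | 14.3.5.3 | 14.3.5.4 | yes |
| ECG interpretation items (13.3.6) | none | none | none |

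The baseline ECG table (14.1.3.5) also covers only QT and QTcF.

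**What per-visit counts can hide**

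Each cohort of 25 is randomized 2:2:1, giving 10, 10 and 5. The two placebo groups pool to 5 + 5 = 10, so one subject is 1/10 = 10 percentage points in every group. Suppose an item reads 2/10 at baseline and 2/10 on Day 29, with all ten subjects observed. If k subjects are common to both visits, the number of new findings is 2 - k. With k = 2, 1 or 0, that is 0, 1 or 2.

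**Which ECG is selected**

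Assume one scheduled ECG within 2 days of target and one further ECG in the same window. If both fall on the same day, the further ECG is taken as the later one. It is selected if it is closer to target, or equally close and later.

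| Window | Scheduled ECG on DY | Further ECG selected if on DY | Left out |
|---|---|---|---|
| Day 15 (DY 2-21, 20 days) | 13 | 13-17 | 15/20 |
| | 14 | 14-16 | 17/20 |
| | 15 | 15 | 19/20 |
| | 16 | 15-16 | 18/20 |
| | 17 | 14-17 | 16/20 |
| Day 29 (DY 22-36, 15 days) | 27 | 27-31 | 10/15 |
| | 28 | 28-30 | 12/15 |
| | 29 | 29 | 14/15 |
| | 30 | 29-30 | 13/15 |
| | 31 | 28-31 | 11/15 |

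The further ECG is left out on 75% to 95% of possible days in the Day 15 window and on 67% to 93% in the Day 29 window. These are shares of calendar days, not probabilities.

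Worked example: an ECG on DY 20 is |20 - 15| = 5 days from target, against at most 2 for the scheduled visit, so it is not selected. If no other ECG falls in the window, the same ECG is tabulated under Day 15.

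**The case against.** The strongest reply is that the findings that matter are reported elsewhere. Protocol 6.4.5 says clinically relevant ECG abnormalities should be reported as adverse events. Those are tabulated by onset after first dosing, without visit selection (SAP 13.1). Exclusion criterion 10 removes clinically significant rate, rhythm or conduction abnormalities at entry. Listing 16.2.12.1 carries every interpretation finding, and Listing 16.2.12.2 sets clinically significant post-baseline data beside the baseline reference. Heart rate, PR and QRS have changes from baseline in Table 14.3.3.2, and pulse has its own shift and worst-case tables. No test rests on Table 14.3.3.6, and the mock tables are a separate document that might show a fuller layout.

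Most of this stands and limits the consequence. It does not remove the gap. The adverse event route and Listing 16.2.12.2 depend on a judgement of clinical relevance or significance, or on QT thresholds. A new arrhythmia judged not significant, with normal QT and on a nonselected ECG, would appear only in the full listing. Numeric intervals and pulse do not classify arrhythmias.

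Three stronger readings are tempting, and the documents do not support them:

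- A reader might infer that unscheduled ECGs are excluded as a class. SAP 4.3 and 4.5 place them in windows. One that is closest to target or alone in its window is tabulated, and a scheduled ECG can be the one left out.
- A reader might infer that there is no baseline information at all. Baseline is a defined time point in SAP 4.3, so group counts at baseline can be shown. Only the within-subject comparison is missing.
- A reader might assume that unscheduled ECGs are the ones most likely to be abnormal. The documents say nothing on this.

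**Conclusion.** The point holds as a limited gap in one safety table. As described in the SAP, Table 14.3.3.6 cannot separate new from pre-existing findings within subjects, and it omits findings seen only on nonselected ECGs. In a group of 10, the first defect leaves a pair of 2/10 counts open to anything from 0 to 2 new findings. The second arises only when two or more ECGs share a window, or when an ECG other than the follow-up visit falls after DY 36. Follow-up ECGs have their own time point and are not lost.

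This does not mean that an arrhythmia would go unreported in the trial, since the adverse event tables and the full listing remain. The conclusion rests on the SAP text, on scheduled visits being held within 2 days of target, and on about 10 subjects per group. It is a low-cost improvement to the summary of a primary-endpoint component, not a threat to the trial's conclusions.

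**What to change.** For each of the four interpretation items, by treatment group, replace the plain frequency with a present/absent shift versus baseline at each time point. Add a row defined as present on any post-baseline ECG, including unscheduled, early-discontinuation and follow-up ECGs, also cross-classified against baseline.

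The any-post-baseline row needs its own definition in SAP 13.3.5 or 13.3.6. The existing rule takes the largest numeric value and cannot be applied to tick-box items.

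The cost is one revised table shell and a short derivation rule, with no new data. The table becomes slightly longer and its cells will be small. One limitation remains: a new, different disorder in a category already ticked at baseline would not register as a shift and would be visible only in the listing.

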13.3.7. Figures

No figures planned.

13.3.8. Listings

Listing 16.2.12.1: ECG: Full listing

Listing per treatment group, per subject and per time point of the ECG parameters (raw values as well as changes from baseline), flagging abnormal results. Includes ECG interpretation and morphology findings.

Population: safety.

Listing 16.2.12.2: ECG: Abnormalities listing

Listing per treatment group, per subject and per time point of all post-baseline data scored as out-of-normal-range (i.e., a QT or QTcF value > 450 ms or a QT or QTcF change > 30 ms) or post-baseline clinically significant, plus also the baseline reference time point.

Population: safety.

13.4. VITAL SIGNS

13.4.1. Available Data

Available parameters: heart rate, respiratory rate, diastolic and systolic blood pressure, temperature and weight.

13.4.2. Baseline and Change from Baseline

The baseline value will be the last nonmissing value prior to first dosing. Baseline will be determined per vital signs parameter individually. It is recognized that baseline parameters may thus come from more than one vital signs reading.

The change from baseline will be calculated for all post-baseline time points as:

Change from baseline at time point t = value at time point t – baseline value.

13.4.3. Normal Ranges

Parameter (unit)	Normal range	
	Lower limit	Upper limit
Pulse (bpm)	40	100
DBP (mmHg)	45	90
SBP (mmHg)	90	150
Temperature (°C)	35.5	37.5
Respiratory rate, breaths/min	12	16

Values equal to the boundaries are still considered normal (N). A value is classified as abnormally low (L) when the value < lower limit of the normal range. A value is classified as abnormally high (H) when the value > upper limit of the normal range.

13.4.4. Worst-Case Abnormality

Derived per parameter separately.

All nonmissing post-baseline values (including unscheduled measurements and follow-up measurements) will be used to derive the following worst-case:

- H = abnormally high:
at least one post-baseline measurement is above the normal range, and there are no values below the normal range.
- L = abnormally low:
at least one post-baseline measurement is below the normal range, and there are no values above the normal range.
- H+L = abnormally high and low:

- at least one post-baseline measurement is above the normal range, and at least one other post-baseline measurement is below the normal range.
- N = normal:
 - all post-baseline measurements are within or equal to normal limits.

13.4.5. Tables

No formal inferential statistics (p-values) will be derived.

Table 14.3.4.1: Vital signs: Descriptive statistics of the actual values per time point

Descriptive statistics of the actual values per test and unit, treatment group and time point.

Population: safety.

Table 14.3.4.2: Vital signs: Descriptive statistics of the changes from baseline per time point

Descriptive statistics of the changes from baseline per test and unit, treatment group and time point. The actual value at baseline will also be presented in this table.

Population: safety.

Table 14.3.4.3: Vital signs: Shift table according to the normal range per time point

Shift table per test, treatment group and time point. The table will present the shift in abnormality (L/N/H) at each post-baseline time point (including worst-case) versus the normal range at baseline (L/N/H).

Population: safety.

Table 14.3.4.4: Vital signs: Treatment-emergent abnormalities per time point

Frequency table of the treatment-emergent abnormalities per parameter, treatment group and time point (including the worst-case). A post-baseline abnormality is considered treatment-emergent if it is different from the baseline result.

Population: safety.

